- **Intervention details:** The first session of the assigned intervention (ASPIRE or GSA-ASPIRE-Network) will occur three to five days after orientation (depending on the ASP's availabilities).
  - › In the ASPIRE condition (other treatment), participants will engage in five 70-minute sessions of ASPIRE spread over a period of 5 weeks (1 session per week). During each session, participants will alternate between 10 minutes of ASPIRE use and 5-minute breaks.
  - › In the GSA-ASPIRE-Network condition (intervention), on the other hand, participants from each club (expected to be between 24 and 50 participants) will be purposely seated in groups, with 3 to 6 adolescents per group. Participants' group allocation will be determined based on findings from social network analysis (details below). Each group will engage in five 70-minute sessions of ASPIRE spread over 5 weeks (1 session per week). During each session, participants will either receive ASPIRE, or the GSAs, or both. Along with the game board, GSA content will be presented to participants via the "Kahoot! 360 Pro" platform. Study data will not be captured nor stored on Kahoot. Participants will not complete any assessment question of identifiable questions via "Kahoot!". They will engage in the program as a team. After each session, with a timeline of a week, participants will have the opportunity to engage in off-session activities at their own pace. These activities will allow participants to practice what they learn during the sessions. To receive credit for completing the activities, participants will be asked to keep track of their progress in these activities and present evidence of completing the activities. To this end and depending on the activities, they may record themselves completing the activity via photo or video and submitting the recording to the research team via the secure system REDCap. Recording and submitting the photos or videos will not be required to participate in the research project, and alternative methods of presenting evidence of activity completion will be provided. If participants choose to submit videos or photos for their activities, they will be asked to capture these videos and photos without having a non-participant in the background. If a non-participant is visible in the background, the recording will be censored to remove the non-participant.

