- **Social network survey:** At all 4 time points, the social network survey will present a list of names of all participants in the classroom. They will be asked to pick and write the names of their six best friends at their club. Best friends are defined to adolescents as "people your age with whom you feel at ease and can talk about personal matters". To measure friendship strength, the survey will ask the respondent to rank nominated friends from strongest to weakest friendship (coded 1 through 6). To measure positive influence, the survey will ask the respondent: (1) how likely he/she may ask each nominated friend for general advice, (2) how likely he/she may accept a tobacco product when offered by each nominated friend (reverse coded), and (3) how likely he/she may avoid a tobacco product when advised by each nominated friend. The strength of a tie between the respondent and each nominated friend will be: Friendship strength × Positive influence. Tie strength will allow the structuring of the social network for each club. Based on the social network at time 1, adolescents will be grouped for their intervention sessions. The survey will also consider participants' nominated advisors and leaders in their ASP. Positive social influence is defined as connection with and support from others who do not intent to use tobacco.
- **Exit Interview questions** (Appendix 5): With adolescents, these questions will address (1) adolescents' most and least favorite elements in the program, (2) their teamwork experience, (3) ways to improve activities, and (4) opportunities for peer-to-peer interaction. With staff members of the ASPs, these questions will address (1) feasibility of the intervention at their location and (2) how they would want to improve the intervention. With intervention implementers, these questions will address (1) feasibility of the intervention, (2) difficulty of implementation, and (3) how they would want to improve implementation.

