Susceptibility to use tobacco is a clinical and epidemiological screening questionnaire of 3 items that has been shown to be the most potent predictor of actual tobacco initiation among adolescents. The continuous version of this scale is termed “intention to use tobacco”. Sample size and power have been calculated based on the hypothesized difference between groups that render participants in the GSA-ASPIRE-Network group non-susceptible to use tobacco, based on the “intention to use tobacco” scale and previous research.

Sample size calculation is done for H1 and satisfies H2. These power estimates are conservative. We will have more power using mixed-effect models. Sample size was calculated based on 2 clusters per arm, however, we will have more power with the proposed 8 clusters (4 clusters per arm). Considering that about 33% of adolescents generally intent to use tobacco, the required sample size is 300 participants. Considering 40% retention and 50 potential non-eligible, we will recruit 800 participants. In addition to this sample size, we will work to reach a representative Florida sample of adolescents. For the interviews, thematic saturation with adolescents is expected by 60 interviews (20% of the final 300 participants).

- **Quantitative data analysis for Study 2.** To test H1, a linear mixed-effect model (LMM) will be conducted to compare the conditions with respect to intention to use tobacco (continuous outcome variable), in a 2 (condition)  $\times$  4 (time) design. Using a second LMM, the 2 conditions will be compared over time with respect to positive social influence. In both models, intervention effects on outcome trajectories over time will be measured with the condition  $\times$  time interaction term. To test H2, a third LMM will be conducted with positive social influence as a mediator. Each individual will be modeled as a random effect nested within the club, club membership will be modeled as a random effect nested within treatment condition, and treatment will be modeled as a fixed effect. If manipulation checks indicate problems, particularly differences or similarities between arms that are not supposed to occur, we will control for such differences or similarities within our models.

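### The Study 2 mixed models have no term for the seating groups that exist in one arm only; if change is correlated within those groups, the H1 test as written and the H2 mediator-to-outcome path are modestly anti-conservative

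*Combined protocol and SAP*

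**What the plan says.** Section 7, Intervention details: in GSA-ASPIRE-Network, the participants of each club ("expected to be between 24 and 50 participants") are "purposely seated in groups, with 3 to 6 adolescents per group" for five weekly 70-minute sessions, and "They will engage in the program as a team". Membership is fixed beforehand. The social network survey item says "Based on the social network at time 1, adolescents will be grouped for their intervention sessions", and Adolescent Grouping matches each at-risk adolescent with 2 to 4 close peers who have no intention to use tobacco.

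For the ASPIRE arm, the same section says that "participants will alternate between 10 minutes of ASPIRE use and 5-minute breaks" and describes no seating groups. Under Study Design, that arm receives the game and network parts only after Assessment 4, outside the 2 × 4 comparison that tests H1.

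Section 7, Quantitative data analysis for Study 2: H1 is tested by the condition × time interaction in a linear mixed model. For H2, "To test H2, a third LMM will be conducted with positive social influence as a mediator". On random effects, "Each individual will be modeled as a random effect nested within the club", and club is nested within condition. The paragraph names no seating-group effect, no random effect of time at any level, no cluster-robust variance and no small-sample degrees of freedom. The sample-size paragraph uses a club ICC of 0.3. No ICC for seating groups appears anywhere.

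**The concern.** The design is partially nested: one arm has a level between adolescent and club, and the other does not. Adolescents who spend five weeks in the same team may change together.

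The H1 test is about change. Random intercepts for individual and club cancel out of change, so the interaction is judged against within-person residual variation. Shared change within a team is then counted as independent evidence, and the standard error is too small.

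H2 can fail in the same way. If positive social influence and intention both vary between teams inside a club, the path from mediator to outcome (path b) is tested as though team-mates were independent. A club-level term does not reach that variation. H2 is the trial's statement of mechanism, so its standard error matters.

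**Working it through.** **The plan's own figure.** Inputs from Sample Size Considerations: 2 clubs per arm, 25 per club, ICC 0.3, difference 2.43 − 1.0 = 1.43, SD 0.8.
- Design effect: 1 + 24 × 0.3 = 8.2.
- Effective n per arm: 50/8.2 = 6.10.
- Standard error: 0.8 × √(2/6.10) = 0.458. Noncentrality: 1.43/0.458 = 3.12.
- A noncentral t on 2 × 6.10 − 2 = 10.2 df gives power 0.804, which reproduces the stated 80%.
- Recruitment also reproduces: 300/0.40 + 50 = 800.

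The only clustering in this calculation is by club.

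**H1 as written.** Assumptions: mean group size m = 4.5, seating-group ICC of change ρ in one arm only, equal arms, no club variance for change. The variance of the arm difference is inflated by V = 1 + (m − 1)ρ/2, where the 2 reflects that only one arm has groups. The true size of a nominal 5% test is 2[1 − Φ(1.96/√V)].

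If 60% of members leave at random after seating, the expected number of remaining team-mates falls from 3.5 to 3.5 × 0.4 = 1.4, which replaces m − 1.

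| ρ | V, intact | Size, intact | V, 40% retained | Size, 40% retained |
|---|---|---|---|---|
| 0.05 | 1.0875 | 6.0% | 1.035 | 5.4% |
| 0.1 | 1.175 | 7.1% | 1.07 | 5.8% |
| 0.2 | 1.35 | 9.2% | 1.14 | 6.6% |
| 0.3 | 1.525 | 11.3% | 1.21 | 7.5% |

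Simulated change scores (8 clubs, 37 per club, groups of 4 to 5) agree for intact groups: about 6%, 7%, 9% and 11%. With 40% random retention, simulation gave 5.6%, 6.7% and 6.9% at ρ = 0.1, 0.2 and 0.3.

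A simulation with all four time points (288 participants, groups of 4, group effects growing after baseline, within-club correlation over time assumed to be 0.6) gave, for linear and 4-level time respectively:
- ρ = 0.1: 8.0% and 6.7%
- ρ = 0.2: 12.2% and 9.0%
- ρ = 0.3: 16.2% and 11.8%

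The size therefore also depends on how time is coded.

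**H1 with a club-level test.** In the four-time simulation, testing club slopes on 6 df (8 clubs) gave 4.5% to 6.2% with no seating-group term. The reverse does not work. If clubs differ in change by only 0.02 to 0.05 of total variance, H1 as written with linear time has 22% to 37% error, and a seating-group term alone leaves it at 17% to 33%.

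**H2 path b, club effects removed.** With the same ρ in mediator and outcome, independent group effects and a true slope of zero, V = 1 + (m − 1)ρ²/2. The ICCs enter as a product, so both variables must cluster.
- ρ = 0.1: V = 1.0175, size 5.2%
- ρ = 0.2: V = 1.07, size 5.8%
- ρ = 0.3: V = 1.1575, size 6.9%

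Simulated change scores gave 5.2%, 5.6% and 7.3%. The four-time simulation gave 5.3%, 6.5% and 9.6%. With 40% random retention, change scores gave 4.9%, 5.1% and 6.3%. Clustering the errors on seating group brought the four-time results to 4.8% to 6.2%.

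**Full mediation claim.** If path b is truly zero and the claim requires both paths to be significant, its false-positive rate cannot exceed that of path b. With path a (condition to mediator) at an assumed 55% to 70% power, simulation gave 3.4%, 3.4%, 4.1% and 4.9% at ρ = 0.1, 0.2, 0.3 and 0.4.

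**The case against.** Four points can be made against this.

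- **H1 needs no seating-group term.** Teams are nested in the randomised clubs, so a club-level test of change with small-sample degrees of freedom already covers them. This stands. The missing club-by-time variation is the larger H1 defect.
- **Path b is not the mediation test.** A reader might infer that the H2 claim itself has too many false positives. The documents do not say how mediation will be tested. If both paths must be significant, the rate stayed below 5% in the settings above. It approaches the path b rate only when path a is well powered. This stands, so the point is limited to the path b standard error.
- **Dropout may thin the groups.** The plan expects 40% retention, and 4.5 × 0.4 = 1.8 members per group leaves little clustering. This stands as a low-end case. The documents do not date the losses, and mixed models keep partial records.
- **The ICC is unsupported.** A reader might take the plan's theory to mean that all team-mates change together, so that the ICC must be large. The Abstract and Adolescent Grouping describe something narrower: change agents moving an at-risk minority, with influence in the other direction meant to be prevented. Members without intention have little room to fall. This stands against any particular value. It does not justify assuming zero after five weeks of teamwork, and mixing at-risk members across teams does not remove shared change.

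**Conclusion.** The omission is plain from the text, and its direction is clear if change is positively correlated within seating groups. Its size is conditional on an ICC that the documents do not give.

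- **H1 as written:** with intact groups of 4 to 5, about 6% false positives at ICC 0.05, 7% at 0.1, 9% at 0.2 and 11% at 0.3. With 60% random loss after seating, about 5% to 7% at ICC 0.1 to 0.3. These figures assume no club variance for change. A club-level test repairs them.
- **H2 path b:** this is the separate contribution. With intact groups the excess is negligible at ICC 0.1; false positives are about 5.5% to 6.5% at 0.2 and 7% to 10% at 0.3, provided that mediator and outcome both vary by seating group.
- **Full mediation claim:** at most about the path b rate.

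The documents do not support saying that the standard errors are too small regardless of the ICC, or that a seating-group term is the only way to protect H1. This is a modest refinement, worth making because it is cheap.

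**What to change.** In Section 7, Quantitative data analysis for Study 2:

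- Keep the club as the unit that sets the degrees of freedom for H1.
- Add a random effect for the seating group assigned at time 1, nested in club, for the GSA-ASPIRE-Network arm only. Treat ASPIRE participants as singletons with no group variance. Use the assigned group, not the group attended.
- Let that effect act on change over time as well as on level. A group intercept alone leaves the condition × time test unchanged.
- For H2, base the standard error of path b on this term, or cluster or resample by assigned seating group.

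The cost is a few sentences and one or two variance parameters. The group identifier already exists from the grouping step. Intervals will be slightly wider, and the group variance may be estimated at zero, in which case little is lost.

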**Figure 1. Study Flow Diagram**

**Note:** Approximate days: Assessment 1 and orientation at day 1 (time 1, baseline), session 1 at 3-5 days after assessment 1, session 2 and assessment 2 (time 2; mid-intervention) at day 12, session 3 at day 19, session 4 and assessment 3 (time 3, post-intervention) at day 26, and assessment 4 (time 4 or assessment 4, follow up) at day 56, assessment 5 at 1 month after assessment 4, Assessment 6 immediately after GSA-Network, assessment 7 at 2-3 weeks later, and assessment 8 at 1 month after A7.

- Instruments for Study 2.** Several variables will be measured through psychosocial (Measures in Appendix 3), and social network surveys (Appendix 4), using previously validated measures delineated below. In a private classroom setting, a study staff or the PI will conduct and collect the surveys and audio recordings.

- **Psychosocial survey:** At all 4 time points, the psychosocial survey will measure tobacco use status and intention to use tobacco. At time 1, this survey will include psychosocial determinants of smoking and factors that may affect an online experience, social influence, social activity engagement, and game play. At time 3 only, the psychosocial survey will include measures to check for any expected differences and similarities between groups (i.e., manipulation check): Attitude toward the intervention, perceived medium interactivity, perceived social interactivity, and perceived entertainment value. To capture adolescents' tendency to positively influence others, the survey will measure interpersonal communication, ability to persuade others, and diffuse health information to others.
- **Social network survey:** At all 4 time points, the social network survey will present a list of names of all participants in the classroom. They will be asked to pick and write the names of their six best friends at their club. Best friends are defined to adolescents as "people your age with whom you feel at ease and can talk about personal matters". To measure friendship strength, the survey will ask the respondent to rank nominated friends from strongest to weakest friendship (coded 1 through 6). To measure positive influence, the survey will ask the respondent: (1) how likely he/she may ask each nominated friend for general advice, (2) how likely he/she may accept a tobacco product when offered by each nominated friend (reverse coded), and (3) how likely he/she may avoid a tobacco product when advised by each nominated friend. The strength of a tie between the respondent and each nominated friend will be: Friendship strength × Positive influence. Tie strength will allow the structuring of the social network for each club. Based on the social network at time 1, adolescents will be grouped for their intervention sessions. The survey will also consider participants' nominated advisors and leaders in their ASP. Positive social influence is defined as connection with and support from others who do not intent to use tobacco.
- **Exit Interview questions** (Appendix 5): With adolescents, these questions will address (1) adolescents' most and least favorite elements in the program, (2) their teamwork experience, (3) ways to improve activities, and (4) opportunities for peer-to-peer interaction. With staff members of the ASPs, these questions will address (1) feasibility of the intervention at their location and (2) how they would want to improve the intervention. With intervention implementers, these questions will address (1) feasibility of the intervention, (2) difficulty of implementation, and (3) how they would want to improve implementation.
- **Adolescent Grouping.** To group adolescents during the GSA-ASPIRE-Network condition (details in Appendix 6), the variable indicating intention to use tobacco will be dichotomized (0=no intention; 1=some intention). At time 1, adolescents who intent to use or are using tobacco will be matched with 2 to 4 adolescents who are closest in distance and do not intent to use tobacco. This ratio is chosen based on previous research showing that 20%-40% of adolescents report some intention to use (average, 33%). If assignment of adolescents to group faces difficulties, we may rely on a continuous measure of intention to use tobacco. Adolescents who indicate intent/use will remain the minority in each group. This design should play a role in preventing at-risk adolescents from influencing their group peers.

The PI along with a statistical analyst and statistician will privately meet in-house at the department in order to make decisions about the intended groupings based on the network data. The study staff will not be present at these meetings. They will be blinded to the basis of the grouping. As a result, they will implement the groupings at the ASPs without knowing the basis of the grouping, thereby insuring that the intended groupings are achieved without disclosing its basis to the participants.

- **Sample Size Considerations for Study 2.** Summary statistics were obtained from the original trial. For H1, given 2 clusters per arm with an average of 25 adolescents who intent to use tobacco in each cluster (n=100) and intra-class correlation (ICC) of 0.3, 80% power is achieved using a two-sided test, with significance  $p<0.05$  to detect a difference in positive social influence in the ASPIRE arm of 1.0 and the GSA-ASPIRE-Network of 2.43 assuming a common standard deviation of 0.8. A difference will be detected

in intention to use tobacco in the ASPIRE arm of 1.3 and GSA-ASPIRE-Network of 0.17 assuming a common standard deviation of 0.5.

Susceptibility to use tobacco is a clinical and epidemiological screening questionnaire of 3 items that has been shown to be the most potent predictor of actual tobacco initiation among adolescents. The continuous version of this scale is termed “intention to use tobacco”. Sample size and power have been calculated based on the hypothesized difference between groups that render participants in the GSA-ASPIRE-Network group non-susceptible to use tobacco, based on the “intention to use tobacco” scale and previous research.

Sample size calculation is done for H1 and satisfies H2. These power estimates are conservative. We will have more power using mixed-effect models. Sample size was calculated based on 2 clusters per arm, however, we will have more power with the proposed 8 clusters (4 clusters per arm). Considering that about 33% of adolescents generally intent to use tobacco, the required sample size is 300 participants. Considering 40% retention and 50 potential non-eligible, we will recruit 800 participants. In addition to this sample size, we will work to reach a representative Florida sample of adolescents. For the interviews, thematic saturation with adolescents is expected by 60 interviews (20% of the final 300 participants).

- **Quantitative data analysis for Study 2.** To test H1, a linear mixed-effect model (LMM) will be conducted to compare the conditions with respect to intention to use tobacco (continuous outcome variable), in a 2 (condition)  $\times$  4 (time) design. Using a second LMM, the 2 conditions will be compared over time with respect to positive social influence. In both models, intervention effects on outcome trajectories over time will be measured with the condition  $\times$  time interaction term. To test H2, a third LMM will be conducted with positive social influence as a mediator. Each individual will be modeled as a random effect nested within the club, club membership will be modeled as a random effect nested within treatment condition, and treatment will be modeled as a fixed effect. If manipulation checks indicate problems, particularly differences or similarities between arms that are not supposed to occur, we will control for such differences or similarities within our models.
- **Qualitative data analysis for Study 2.** Qualitative data analysis will be conducted to answer the research question RQ2. The audio-recordings of the interviews and intervention sessions will be transcribed verbatim by the study staff or by a professional transcription service. Then, the data will be analyzed using techniques described by Stewart and Shamdasani. The transcripts will be read independently by two study team members and major emerging themes will be identified. Following the identification of themes, inter-coder reliability will be conducted. The sessions will allow for the exploration of relevant adolescents’ experience with the intervention, gaming features that are salient to adolescents, and how the design of the activities should be reshaped for better outcomes. Themes will be defined as psychological, social, or emotional experiences of adolescents, and issues or ideas that are repeated and common to several participants in a group.

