### 3. Abstract:

- **Problem:** Negative influence from peers and friends is a well-known potent predictor of adolescent smoking initiation. However, what is not known is how to design and implement an intervention that promotes positive social influence for adolescents (i.e., connection with and support from others who do not intent to use tobacco). One example of an intervention that lacks positive social influence is a Web-based, computer-tailored intervention called *A Smoking Prevention Interactive Experience* (ASPIRE).
- **Potential solution:** One innovative approach to fill the gap is to apply social influence strategies. First, game-based social activities (GSAs) can facilitate exploration of health information and drive social discussions against tobacco use. Second, social network analysis allows us to strategically group at-risk adolescents (i.e., those who use or intend to use tobacco) with close peers who do not intend to use tobacco (i.e., change agents), as they engage in ASPIRE. Change agents will positively influence at-risk adolescents for two reasons: (1) At-risk adolescents will be dominated in number by change agents, and (2) their interaction with change agents will be directed by the healthy content of ASPIRE and the GSAs.
- **Objective and central hypothesis:** The objective of the current research is to identify the effect of ASPIRE on key mechanisms underlying adolescents' intention to use tobacco products (cigarettes, cigars, hookah water pipes, and vaping products), when social influence strategies are added to the intervention. The central hypothesis is that the addition of social influence strategies to ASPIRE will boost ASPIRE's success in lowering intention to use tobacco.
- **What we will do:** Through focus group discussions, we will improve designed GSAs (Study 1). Then, through a group-randomized study (Study 2), we will compare the use of ASPIRE alone (ASPIRE) with the use of GSAs along with ASPIRE and social grouping using social network analysis (GSA-ASPIRE-Network). This study will be conducted with after-school or school programs (ASPs) in Florida.

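### Friendship rank is coded 1 for the closest friend and then multiplied by positive influence, so the two factors of tie strength pull in opposite directions; the rank needs reversing before groups are formed

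*Combined protocol and SAP*

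**What the plan says.** The relevant text is in Section 7, under Instruments for Study 2 (Social network survey) and Adolescent Grouping.

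- Each respondent is asked to "pick and write the names of their six best friends at their club" and then to "rank nominated friends from strongest to weakest friendship (coded 1 through 6"). This is the friendship-strength variable.
- Positive influence has three items per friend. The first is "how likely he/she may ask each nominated friend for general advice". The second, accepting tobacco when the friend offers it, is marked as reverse coded. The third is avoiding tobacco when the friend advises it.
- The two are combined as a product: "The strength of a tie between the respondent and each nominated friend will be: Friendship strength" multiplied by positive influence.
- The result structures each club's network, and "Based on the social network at time 1, adolescents will be grouped for their intervention sessions".
- Under Adolescent Grouping, at-risk adolescents are "matched with 2 to 4 adolescents who are closest in distance and do not intent to use tobacco". Further detail is deferred: "To group adolescents during the GSA-ASPIRE-Network condition (details in Appendix 6").
- The Abstract gives the purpose, which is to place at-risk adolescents "with close peers who do not intend to use tobacco (i.e., change agents").

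**The concern.** A product of two scores measures tie strength only if both rise with strength. Here influence rises with strength and the rank falls with it. The paragraph states a reversal for the tobacco-acceptance item but none for the rank, so an analyst who follows the text would give the largest ties to the least close of the nominated friends.

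The score has a real use. It feeds the baseline network, which decides who sits with whom in the experimental arm, and grouping at-risk adolescents with close non-intending peers is a defining part of that arm. If the groups were formed from a mis-oriented score, a null result could reflect the scoring rather than the strategy. Study staff are blinded to the basis of the grouping, so those who seat the adolescents are poorly placed to notice.

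**Working it through.** The plan gives no figure to reproduce. The check compares the rule as written with a consistently oriented rule.

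**Inputs from the plan (Section 7, Social network survey).** Six nominated friends. Rank r = 1 (strongest) to 6 (weakest). Positive influence P, higher being more positive: items 1 and 3 run that way as asked, and item 2 does after its stated reversal.

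**Formulas.** As written: T = r × P. Consistently oriented: T* = (7 − r) × P.

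**Step 1: equal influence, no scale needed.** For any P > 0, the sixth friend scores 6P and the best friend 1P, a ratio of 6. With P = 5, T is 5, 10, 15, 20, 25, 30 from closest to least close, and T* is 30, 25, 20, 15, 10, 5.

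**Step 2: the distance reading.** Suppose a small product means close. The rank then runs the right way, but a friend with higher P becomes more distant. One factor has to be reversed under either reading. Since the text calls the product the strength of a tie, that factor is the rank.

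**Step 3: extreme cases.** The best friend at maximum influence scores 1 × max; the sixth friend at minimum influence scores 6 × min. Whenever max < 6 × min, the best friend can never outscore the sixth. This holds on 1–4 (4 < 6), on 1–5 (5 < 6) and on a three-item sum of 3–15 (15 < 18). It does not hold on 1–7 (7 > 6) or 0–10 (10 > 0).

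**Step 4: how often the order changes.** The response scale for influence is not in the document, so five scales are assumed. All combinations of rank and integer influence are enumerated. Pairs of different rank are compared, dropping pairs tied on either score. The last column simulates 400,000 respondents with six friends each, influence uniform on the scale and independent of rank, ties broken at random. It gives the share whose two strongest ties under T and under T* have no friend in common.

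| Assumed scale | Pairs in opposite order | Spearman, T with T* | Two strongest ties: none in common |
|---|---|---|---|
| 1–4 | 138/216 = 64% | −0.10 | 61% |
| 1–5 | 209/343 = 61% | −0.03 | 60% |
| 1–7 | 395/685 = 58% | +0.06 | 57% |
| 0–10 | 784/1718 = 46% | +0.33 | 46% |
| 3–15 | 1617/2447 = 66% | −0.19 | 68% |

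Two friends drawn at random from six would miss both of a given two with probability C(4,2)/C(6,2) = 6/15 = 40%. If influence instead falls with rank, so that closer friends are also more influential, the no-overlap share is 62% to 89%. In no case do the two scores pick the same two friends in more than 4.7% of respondents, against 1/15 = 6.7% for a random draw.

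**Sensitivity to the denominator.** Adding same-rank pairs, which cannot be reversed, lowers the 1–5 figure to 209/403 = 52%. Adding tied pairs as well gives 209/435 = 48%, and on 0–10 784/2145 = 37%.

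**The case against.** **The direction is not spelled out.** The text never says that 1 means strongest, and a variable called friendship strength might have been meant with 6 as strongest. That is possible, but it runs against the order of the sentence. If it was the intention, the sentence still needs correcting. A blind reversal would create the error if the data already hold 6 for the strongest, so the fix must name the end state and not merely the operation.

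**The operational detail may be elsewhere.** The survey is in Appendix 4 and the grouping details in Appendix 6, neither of which is in the public document. Either may reverse the rank. This stands, and it limits the point to the rule as written in the main text.

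**The simulation is not the grouping rule.** This also stands. Distance is undefined. If it is path length in an unweighted nomination network, all six nominees are one step away and the coding does not affect which of them is nearest. Candidates are restricted to non-intenders, groups hold 3 to 6, at-risk members must stay a minority, and the investigator, an analyst and a statistician settle the groups in a meeting. The percentages describe how far the two scores disagree. They do not estimate how many adolescents would be misplaced.

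**The size depends on the assumed scale.** It does: on 0–10 the two scores correlate positively (+0.33), and the no-overlap share is not far above the random 40%. A uniform distribution is also a rough stand-in for a sum of three items. The six-fold ratio in step 1 needs no scale.

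**The consequence is limited.** Every tie still links a respondent to a named best friend. The planned models analyse intention to use tobacco and positive social influence, and tie strength is not named as an outcome or a model term.

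**Conclusion.** The concern holds. As written, the two factors of tie strength run in opposite directions, and neither the strength reading nor the distance reading reconciles them. This follows from the wording and needs no assumption beyond reading the rank in the order stated.

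At equal non-zero influence the least close of six friends gets six times the tie of the closest. Over the five assumed scales, 46% to 66% of untied different-rank pairs change order. The effect on actual seating cannot be given, because distance is undefined and the appendices are not available.

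The consequence is for the fidelity of the Network component: followed literally, the rule could seat at-risk adolescents with less close or less influential friends. The randomised comparison of the whole package remains valid, and the stated sample-size inputs do not depend on this coding. It should be fixed, but it does not threaten the trial's primary inference.

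**What to change.** 1. In the Social network survey paragraph, state that friendship strength enters the product with 6 = strongest and 1 = weakest, that is 7 − rank when the survey records 1 for the strongest. If the data are already held with 6 as strongest, correct only the sentence.
2. Under Adolescent Grouping, define distance and make it a decreasing function of the corrected tie strength. If an unweighted path length is intended, say so and say what tie strength is used for.
3. Confirm that both paragraphs agree with Appendices 4 and 6.
4. If groups have already been formed, check which coding was used and report it with the results.

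The cost is one line of coding, a few words of protocol text and a check against two appendices. No new data are needed.
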